#### 10.6 Response Criteria for Neuroblastoma Patients

Response criteria follow the revised INRC criteria with special consideration for possible pseudo-progression (Park, 2017). Assessment will include anatomic imaging for primary and metastatic soft tissue disease, nuclear medicine imaging using I-MIBG or FDG-PET for assessment of soft tissue and bone disease and BM aspirates/ trephine biopsies are recommended for assessment of marrow disease at the discretion of the local treating physician (Park, 2017). Tissue biopsies may be used as an adjunct to verify the presence of viable neuroblastoma or ganglioneuroblastoma that is evaluable for response. Urine catecholamine levels will not be used to evaluate response because of a lack of standardization in specimen collection and analysis and the influence of diet on results (Park, 2017).

# 10.6.1 Neuroblastoma Patients with Primary and Metastatic Soft Tissue Disease

To assess primary and metastatic soft tissue tumor response in most patients. MIBG uptake (or FDG for tumors that are not MIBG-avid) will be used to determine which metastatic soft tissue lesions considered measurable by iRECIST will be deemed target lesions for assessment of response.

**MIBG Positive Lesions:** Patients who have a positive MIBG scan at the start of therapy will be evaluable for MIBG response. The use of I-MIBG imaging is recommended for all scans. If the patient has only one MIBG positive lesion and that lesion was radiated, a biopsy must be done at least 28 days after radiation was completed and must show viable neuroblastoma.

MIBG Negative Lesions: Patients whose tumors do not concentrate MIBG, FDG-PET is an alternative modality for tumor detection, although FDG is less specific than MIBG because of uptake of FDG in inflammatory lesions, as well as normal and cytokine-stimulated BM (Park, 2017; Tsai, 2017). Less specific for neuroblastoma, a tissue biopsy of at least one of the lesions may be required to confirm that FDG-avid, MIBG-non-avid lesions are histologically confirmed to be neuroblastoma and/or ganglioneuroblastoma. Increased FDG avidity in lymphoid tissue associated with response to ICIs and may give the initial impression of disease progression (Tsai, 2016). Increased FDG uptake in benign lymphoid tissue seen on PET/CT may be a surrogate

marker of immune activation and treatment response, although more prospective studies are necessary (Cho, 2017).

The following terms will be used to define neuroblastoma primary and metastatic soft tissue lesions:

**Target lesions (TL):** Disease sites (non-lymphoid soft tissue or lymph node) that meet the criteria of measurable size  $\geq 10$  mm in the longest dimension or  $\geq 15$  mm in short axis, respectively.

• Either uptake on MIBG or FDG for MIBG-non-avid tumours (with recommended biopsy) or biopsy positive for neuroblastoma or ganglioneuroblastoma.

Non-Target Lesions (NTL): Lesions that are active tumour sites but do not meet TL criteria.

- Non-target soft tissue lesions will include leptomeningeal, cerebrospinal fluid, ascites, or
  pleural effusion tumours and lesions smaller than 10 mm that are considered likely to be
  active tumor based on clinical correlation;
- Small soft tissue lesions and lymph nodes that measure shorter than 15 mm on short axis
  will be considered non-target lesions if they are biopsied and proven to consist of viable
  tumor;
- Non-lymph node soft tissue lesions at least 10 mm in diameter and lymph nodes larger than 15 mm on short axis that are not MIBG or FDG avid and do not contain viable tumor (if biopsied) will not be considered either target or non-target lesions.

**Discrete Lymph Node:** Single lymph node that can be discretely identified (i.e. cervical node); measured by short axis.

**Sum of Diameters:** Sum of the shortest axis of discrete lymph nodes added to the sum of the longest diameter on non-lymph node soft tissue metastases;

 Conglomerate masses of non-discrete lymph nodes will be measured using longest diameter.

### 10.6.2 Primary Tumour

The following criteria will be used to report anatomic and MIBG (or FDG-PET in non-MIBG-avid lesions) imaging response by the treating institution:

**Complete Response (CR):** Less than 10 mm residual soft tissue at primary site.

• Complete resolution of all MIBG or FDG-PET uptake at primary site.

Partial Response (PR): Greater than 30% decrease in the longest diameter of the primary site.

• MIBG or FDG-PET uptake at primary site stable, improved or resolved.

**Stable Disease (SD):** Neither sufficient shrinkage for PR nor sufficient increase for PD at the primary site.

**Unconfirmed progressive disease (iUPD):** The increase in uptake intensity/ appearance of one or more lesions or evidence of laboratory, clinical, or radiographic progression. iUPD must be assessed between four to eight weeks to confirm progression and become iCPD.

**Confirmed progressive disease (iCPD):** iUPD must be assessed between four to eight weeks to confirm progression and be deemed as iCPD

**Progressive Disease (PD):** Development of new MIBG positive lesions.

- Greater than 20% increase in the longest diameter taking as a reference the smallest sum on study (including baseline)
- Minimum absolute increase of 5 mm in longest dimension
- Mass does not meet PD measurement criteria, but has fluctuating MIBG avidity will not be considered PD.
- The response of MIBG lesions will be assessed on central review using the Curie scale (Ascierto, 2011).
- Central review responses will be used to assess efficacy for study endpoint. As such the iUPD nomenclature does not apply.

Note: This scoring should also be done by the treating institution for end of course response assessments.

#### 10.6.3 Metastatic Soft Tissue and Bone Disease

I-MIBG uptake will be used for evaluation of response at osteomedullary lesions (Park, 2017). For patients whose tumors do not concentrate MIBG, FDG-PET or PET/CT scan will be used for tumor detection in bone. Anatomic imaging will not be used to evaluate osteomedullary lesions, because these lesions may not shrink in size using CT/MRI even in the absence of residual viable tumor. Additionally, osseous lesions without a soft tissue mass are considered non-

measurable by standard RECIST criteria. The measurable extramedullary soft tissue components of bone lesions will be assessed using the same criteria used for other soft tissue sites (see *Section* 10.5.1).

[figure not shown]
The body is divided into 9 anatomic sectors for osteomedullary lesions, with a 10th general sector allocated for any extra-osseous lesion visible on MIBG scan. In each region, the lesions are scored as follows. The absolute extension score is graded as by adding the score of all segments (*Figure 3*):

0 = no site per segment

1 = 1 site per segment

2 = more than one site per segment

3 = massive involvement (>50% of the segment)

**Figure 3.** Absolute Score anatomic sectors diagram for osteomedullary lesions, with a 10th general sector allocated for any extra-osseous lesion visible on MIBG scan.

The relative score is calculated by dividing the absolute score at each time point by the corresponding pre-treatment absolute score. The relative score of each patient is calculated at each response assessment compared to baseline and classified as below (Park, 2017):

Complete Response (CR): All areas of uptake on MIBG scan completely resolved, defined as:

- Non-primary target and non-target lesions measure < 10mm;
- Lymph nodes identified as target lesions decrease to a short axis < 10 mm;
- MIBG uptake or FDG-PET uptake (for MIBG-non-avid lesions) of non-primary lesions resolves completely.

**Partial Response (PR):**  $\geq 30\%$  decrease in sum of diameters (see above for definition) of non-primary target lesions compared with baseline, and all of the following:

- NTL may be stable or smaller in size;
- No new lesions;
- $\geq$  50% reduction in MIBG absolute bone score (relative MIBG bone score  $\geq$  0.1 to  $\leq$  0.5; see *Figure 3*)  $\geq$  50% reduction in the number of FDG-PET-avid bone lesions.
  - For patients with soft tissue metastatic disease, resolution of MIBG and/or FDG-PET uptake at the soft tissue sites is not required, but all size reduction criteria must be fulfilled;

**Stable Disease (SD):** Neither sufficient shrinkage for PR nor sufficient increase for PD of non-primary lesions.

**Progressive disease (PD):** Any of the following:

- Any new soft tissue lesion detected by CT/MRI that is also MIBG avid or FDG-PET avid;
- Any new soft tissue lesion seen on anatomic imaging that is biopsied and confirmed to be neuroblastoma or ganglioneuroblastoma;
- Any new bone site that is MIBG avid;
- A new bone site that is FDG-PET avid (for MIBG-non-avid tumours) and has CT/MRI findings consistent with tumour or has been confirmed histologically to be neuroblastoma or ganglioneuroblastoma;
- >20% increase in longest diameter taking as reference the smallest sum on study (this
  includes the baseline sum) and minimum absolute increase of 5 mm in sum of diameters
  of target soft tissue lesions;

- Relative MIBG score  $\geq 1.2$ .
- The response of MIBG lesions will be assessed on central review using the Curie scale (Ascierto, 2011).
- Central review responses will be used to assess efficacy for study endpoint. As such the iUPD nomenclature does not apply.

Note: This scoring should also be done by the treating institution for end of course response assessments.

# 10.7 Response Criteria for Neuroblastoma Patients with Metastatic Bone Marrow Involvement

Assessment of BM involvement is achieved via evaluation of bilateral aspirates and bilateral trephine biopsies, a total of four (4) sampled sites. Assessment of BM for neuroblastoma cells must use morphologic criteria in conjunction with appropriate antibodies to confirm the identity of neuroblastoma cells by immunocytology (if available) and/or IHC (Park, 2017). Only BM samples of suitable quality should be investigated, as specified by Burchill, *et al.* (2016). Exact quantification of BM involvement at all sites should be reported; the percentage of tumor infiltration of BM space assessed by histologic evaluation divided by the number of hematopoietic or mononuclear cells evaluated to obtain a percentage of involvement (methodology described by Burchill, *et al.* (2016). The BM sample with the highest percentage of tumor infiltration is used in the response algorithm. BM must be obtained within 28 days prior to study enrollment with tumour cells seen on routine morphology. Response will be compared with baseline disease evaluations before enrollment in **Part II**.

Neuroblastoma infiltration in the marrow can be heterogeneously distributed throughout the skeleton (Park, 2017). Due to the clinical impact of this heterogeneity, detection of more than 0% to  $\le 5\%$  tumor infiltration in BM will represent a new category of minimal disease. See below for BM metastasis response definitions determined by cytology/ histology:

**Complete Response** (CR): BM with no tumour infiltration on reassessment, independent of baseline tumour involvement.

**Progressive disease (PD):** Any of the following, detected in 2 consecutive BM biopsies or aspirations done at least 21 days apart:

- BM without tumour infiltration that becomes > 5 % tumour infiltration on reassessment;
- BM with tumour infiltration that increases by > 2x and has > 20 % tumour infiltration on reassessment.

### Minimal Disease (MD): Any of the following:

- BM with  $\leq 5\%$  tumour infiltration and remains > 0 to  $\leq 5\%$  tumour infiltration on reassessment;
- BM with no tumour infiltration that has  $\leq 5\%$  tumour infiltration on reassessment;
- BM with > 20% tumour infiltration that has > 0 to  $\le 5\%$  tumour infiltration on reassessment.

**Stable Disease (SD):** BM with tumour infiltration that remains positive with > 5% tumour infiltration on reassessment but does not meet CR, MD, or PD criteria.

Note: In the case of discrepant results between aspirations/ biopsies from two or more sites taken at the same time, the highest infiltration result should be reported.

## 10.7.1 Best Overall Response (iBOR)

The best overall response is the best response recorded from the start of the treatment until disease progression/ recurrence (taking as reference for progressive disease the smallest measurements recorded since the treatment started). The patient's best response assignment will depend on the achievement of both measurement and confirmation criteria. See *Tables 6-9* for details. All iUPD require re-evaluation four to eight weeks later to confirm disease progression (iCPD).

Best overall response will be determined by combining response of the individual components (i.e., soft tissue, bone, and BM disease). All components must be evaluated and of sufficient quality to fully assess overall response. An overall CR requires that all involved components have a CR. An overall PR includes a PR of all soft tissue and bone sites or non-involvement in one of these components, but allows residual MD in the bone marrow. Minor response (MR) requires PR or CR in at least one component, SD for at least one component, and no evidence of progressive disease in any component. PD in any one component defines overall PD.

**Best Overall Response (BOR):** Each patient will be classified according to his "best response" for the purposes of analysis of treatment effect. Best response is determined from the sequence of the overall response assessments as described below.

**Table 5.** Evaluation of Best Overall Response (iBOR) for Patients with Measurable Disease (i.e., Target Disease).

Lesions	Non-Target	New	Overall	Best Overall Response when
	Lesions	Lesions	Response	Confirmation is Required*
CR	CR	No	CR	≥ 28 days Confirmation
CR	Non-	No	PR	
	CR/Non-PD			≥ 28 days Confirmation
CR	Not evaluated	No	PR	
PR	Non-	No	PR	
	CR/Non-			
	PD/not			
	evaluated			
SD	Non-	No	SD	documented at least once $\geq 28$ days from
	CR/Non-			baseline
	PD/not			
	evaluated			
iUPD	Any	Yes or No	iCPD/PD	
				no prior SD, PR or CR
Any	iUPD**	Yes or No	iCPD/PD	
Any	Any	Yes	PD	

\* See iRECIST manuscript for further details on what is evidence of a new lesion (Seymour, 2017).

\*\* In exceptional circumstances, unequivocal progression in non-target lesions may be accepted as disease progression.

Note: Patients with a global deterioration of health status requiring discontinuation of treatment without objective evidence of disease progression at that time should be reported as "symptomatic deterioration." Every effort should be made to document the objective progression even after discontinuation of treatment.

**Table 6.** Evaluation of Best Overall Response for Patients with Non-Measurable Disease (i.e., Non-Target Disease).

Non-Target Lesions	New Lesions	Overall Response
CR	No	CR
Non-CR/non-PD	No	Non-CR/non-PD
Not all evaluated	No	not evaluated
Unequivocal PD	Yes or No	PD
Any	Yes	PD

\* 'Non-CR/non-PD' is preferred over 'stable disease' for non-target disease since SD is increasingly used as an endpoint for assessment of efficacy in some trials so to assign this category when no lesions can be measured is not advised

**Table 7.** Sequences of overall response assessments with corresponding best response.

1st Assessment	2nd Assessment	Best Response
IUPD	iCPD	PD
Stable, PR, CR	iUPD	Requires reassessment 4 - 8 weeks.
Stable	Stable	Stable
Stable	PR, CR	Stable
Stable	Not done	Not RECIST classifiable
PR	PR	PR
PR	CR	PR
PR, CR	Not done	Not RECIST classifiable
CR	CR	CR

Table 8. Overall Response for Patients with Neuroblastoma and Measurable Disease.

CT/MRI	MIBG	BM	Catecholamine	Overall
iUPD	Any	Any	Any	
Any	iUPD	Any	Any	PD
Any	Any	Any	Any	PD
Any	Any	iUPD	Any	PD
SD	CR/PR/SD	Non-PD	Any	SD
PR	CR/PR	Non-PD	Any	PR
CR/PR	PR	Non-PD	Any	PR
CR	CR	Non-PD	Elevated	PR
CR	CR	CR	Normal	CR

**Table 9.** Overall Response Evaluation for Neuroblastoma Patients and MIBG Positive Disease.

MIBG	CT/MRI	BM	Catechol	Overall
iUPD	Any	Any	Any	PD
Any	New Lesion	Any	Any	PD
Any	Any	Any	Any	PD
Any	Any	iUPD	Any	PD
SD	No New Lesion	Non-PD	Any	SD
PR	No New Lesion	Non-PD	Any	PR
CR	No New Lesion	Non-PD	Elevated	PR
CR	No New Lesion	CR	Normal	CR

• Only if patients are enrolled without disease measurable by CT/MRI, any new or newly identified lesion by CT/MRI that occurs during therapy would be considered progressive disease and not unconfirmed immune-progressive disease (iUPD) requiring reassessment to be diagnosed as iCPD.

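### Neuroblastoma response rules conflict on whether an unconfirmed progression (iUPD) is already overall PD, so a flare followed by a confirmed response can be scored either way

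*Protocol*

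**What the plan says.** The lead text of section 10.6 announces an allowance for flare: "Response criteria follow the revised INRC criteria with special consideration for possible pseudo-progression". Four sets of passages then deal with a first, unconfirmed progression.

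- **Confirm first.** Section 10.7.1: "All iUPD require re-evaluation four to eight weeks later to confirm disease progression (iCPD"). Table 7 gives PD for iUPD followed by iCPD and asks for reassessment when iUPD follows SD, PR or CR. The note to Table 9 makes immediate PD an exception. Only for patients enrolled without disease measurable on CT or MRI is a new CT/MRI lesion one that "would be considered progressive disease and not unconfirmed immune-progressive disease (iUPD) requiring reassessment".
- **PD at once.** Table 8 has the row "Any iUPD Any Any PD" (iUPD on MIBG) and the row "Any Any iUPD Any PD" (iUPD in marrow). Table 9, headed "Overall Response Evaluation for Neuroblastoma Patients and MIBG Positive Disease", also gives overall PD for iUPD on MIBG and for iUPD in marrow. No column or footnote adds a confirmation step to these rows.
- **iUPD not used.** Section 10.6.2 defines iUPD and iCPD with the four-to-eight-week check, then ends: "Central review responses will be used to assess efficacy for study endpoint. As such the iUPD nomenclature does not apply". Section 10.6.3 repeats this. Its own list of metastatic PD criteria, such as a relative MIBG score of 1.2 or more, has no confirmation step.
- **Marrow.** Section 10.7 calls marrow PD only when it is found in two successive samples taken 21 days or more apart. It defines no marrow iUPD.

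**The concern.** ORR is the primary endpoint, and checkpoint inhibition is the setting in which early apparent progression may be inflammatory. Section 10.7.1 counts best response only up to progression and makes progression in a single component overall PD. A PD call at the flare visit therefore shuts out any later response and creates a PFS event. If the call is held open until the check at four to eight weeks, a later response can still count. Two analysts working correctly from different pages could give the same patient opposite classifications, and could do so after seeing the outcome.

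**Working it through.** The point is about wording, so the main check follows one patient through the passages. The arithmetic only shows how much one classification can matter.

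**Patient path.** Neuroblastoma; the first disease evaluation shows iUPD on MIBG; the next shows PR or CR; this response is confirmed at least 28 days later, as section 10.2 and Table 5 require.

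| Passage applied | Flare visit | Best response | PFS |
|---|---|---|---|
| Table 8 or 9, MIBG iUPD row | PD | PD | event |
| 10.6.2 / 10.6.3, iUPD not used | PD if the PD criteria are met | PD | event |
| 10.7.1 with 10.4.1 | iUPD, unconfirmed | PR or CR | no event at the flare |

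The last row needs 10.4.1. Section 10.7.1 says the iUPD must be confirmed, but Table 7 has no row for iUPD followed by PR or CR. The rule that iUPD does not override a later response stands in 10.4.1.

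**Marrow variant.** The natural reading of iUPD in the marrow column is a first positive sample not yet repeated. Section 10.7 says that is not PD; Tables 8 and 9 say it is.

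**Effect of one patient on the decision rules.** Inputs from section 11: Cohort A rejects at 5 or more of 20 and Cohort B at 6 or more of 30. Each closes at 1 or fewer of the first 10.

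- Stage 1, either cohort: 2 of 10 continues; 2 − 1 = 1 of 10 closes.
- Final, Cohort A: 5 of 20 rejects; 5 − 1 = 4 does not.
- Final, Cohort B: 6 of 30 rejects; 6 − 1 = 5 does not.

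**Effect on the Bayesian summary.** Section 11 specifies non-informative priors without naming one. With a uniform prior, x responses in n patients give a Beta(1 + x, 1 + n − x) posterior. This reproduces the protocol's own figures for P(RR > 0.2): 0.77 at 5/20 and 0.57 at 6/30. Removing one response:

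| Result | Posterior | P(RR > 0.2) | P(RR < 0.1) |
|---|---|---|---|
| 5/20 | Beta(6, 16) | 0.77 | 0.01 |
| 4/20 | Beta(5, 17) | 0.59 | 0.05 |
| 6/30 | Beta(7, 25) | 0.57 | 0.03 |
| 5/30 | Beta(6, 26) | 0.39 | 0.08 |

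**Not relied on.** In the text at hand, the Overall cell of the CT/MRI iUPD row in Table 8 is blank, and both tables show a row reading Any in every column with PD as the result. Either may be a fault of text extraction. The MIBG and marrow rows are enough.

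**The case against.** The best defence reads the passages together. Section 10.7.1 refers to Tables 6 to 9 for detail, states the confirmation rule in the next sentence, and takes best response from the sequence of assessments, for which Table 7 is the key. Tables 8 and 9 would then be time-point entries subject to that rule. This does not hold. Table 5 writes iCPD/PD in its iUPD rows, while Tables 8 and 9 write plain PD, and PD in one component closes the best-response window.

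A second defence is that central review sets the endpoint and iUPD is only a local label. But 10.7.1 says its best-response classification is made for the analysis of treatment effect, and it requires confirmation there. If central review does drop iUPD, the allowance announced in 10.6 has no bearing on the endpoint.

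Several limits stand. A reader might infer more than the documents support:

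- *That section 10.6 as a whole rules out iUPD.* Its lead text says the opposite; the sentence is confined to 10.6.2 and 10.6.3.
- *That 10.7.1 alone makes the patient a responder after one good scan.* The result depends on 10.4.1, written for solid tumours with measurable disease, and on confirmation at 28 days or more.
- *That PFS dates move for every neuroblastoma progressor.* The conflict bears on patients whose progression is not confirmed. No shift is shown for confirmed progression, and the general iRECIST text uses the initial date in some situations (10.2.5, 10.2.7).
- *That the loss of ORR or power can be sized.* The protocol gives neither the neuroblastoma share nor a flare rate. A cohort must also sit exactly at its cut-off for one patient to decide it.

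**Conclusion.** The inconsistency is real and touches the primary endpoint. For a neuroblastoma patient with an unconfirmed flare and then a confirmed PR or CR, the protocol supports both non-responder with a PFS event and responder. The size is one response per such patient, and their number is unknown. One is enough to reverse a cohort's conclusion at 5 of 20 or 6 of 30, or to close a cohort at 2 of 10. Nothing here shows that the trial's ORR is materially biased; the effect is confined to a subset that the documents do not quantify. The conclusion rests on the table rows reading as they appear in the text at hand, and on marrow iUPD meaning a first, unrepeated sample. It is worth correcting because it is cheap to settle in advance and hard to settle impartially once such a patient exists.

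**What to change.** Reconcile the passages so that one rule sets overall response, best response and PFS date in neuroblastoma for the endpoint analysis.

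To agree with 10.7.1 and the pseudo-progression allowance in 10.6, Tables 8 and 9 would score overall PD only on confirmed progression (iCPD). The marrow rows would follow the two-sample definition in 10.7, and the note to Table 9 would remain the stated exception. If the sponsor instead intends no confirmation for the endpoint, it should say so once and amend 10.7.1, Table 7 and the lead text of 10.6.

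Replacing iUPD by iCPD in the two tables is not enough. Whichever rule is kept, these must be aligned with it: the closing sentence of 10.6.2 and 10.6.3, the PD list in 10.6.3, the New Lesion row of Table 9, and the rule in 10.7.1 that PD in a single component makes overall PD. A row for iUPD followed by confirmed PR or CR should be added to Table 7.

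Confirmed progression also governs stopping of treatment elsewhere in the protocol. Any consequence there is for the sponsor to reconcile and is not prescribed here.

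Cost: wording in an amendment. No new assessments are needed, since re-evaluation at four to eight weeks is already required.

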## **10.4.2** Evaluation of Target Lesions

Complete Response (CR): Disappearance of all target and non-target lesions. Any pathological lymph nodes (whether target or non-target) must have reduction in short axis to <10 mm. If immunocytology is available, no disease must be detected by that methodology. Normalization of urinary catecholamines or other tumour markers if elevated at study enrollment (for patients with neuroblastoma).

**Partial Response (PR):** At least a 30% decrease in the sum of the diameters of target lesions, taking as reference the baseline sum diameters

Unconfirmed progressive disease (iUPD): At least a 20% increase in the sum of the diameters of target lesions, taking as reference the smallest sum on study (this includes the baseline sum if that is the smallest on study). In addition to the relative increase of 20%, the sum must also demonstrate an absolute increase of at least 5 mm. iUPD must be assessed between four to eight weeks to confirm progression and become iCPD.

Confirmed progressive disease (iCPD): iUPD must be assessed between four to eight weeks to confirm progression and be deemed as iCPD. There must be at least a 20% increase in the sum of the diameters of target lesions, taking as reference the smallest sum on study (this includes the baseline sum if that is the smallest on study). In addition to the relative increase of 20%, the sum must also demonstrate an absolute increase of at least 5 mm.

**Progressive Disease (PD):** New Lesion if the next imaging assessment, conducted at least four (4) weeks, but not more than eight (8) weeks after iUPD confirms further progression from iUPD with either an increase of at least 5 mm in the absolute value of the sum of NLT or an increase (but not necessarily unequivocal increase) in the size of NLNT lesions OR the appearance of additional new lesions.

**Note:** In presence of SD or PR in target disease but unequivocal progression in non-target or non-measurable disease, the patient has PD if there is an overall level of substantial worsening in non-target disease such that the overall tumour burden has increased sufficiently to merit discontinuation of therapy.

**Stable Disease (SD):** Neither sufficient shrinkage to qualify for PR nor sufficient increase to qualify for iUPD or PD, taking as reference the smallest sum diameters while on study.

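### Neuroblastoma overall response is defined inconsistently: with marrow stable disease, the same patient can be a non-responder by the 10.7.1 text and a responder by Tables 8 and 9

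*Protocol*

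**What the plan says.** **Overall response, text of 10.7.1.** "An overall PR includes a PR of all soft tissue and bone sites or non-involvement in one of these components, but allows residual MD"; the residue that may remain is marrow disease. The rule for the next lower category reads: "Minor response (MR) requires PR or CR in at least one component, SD for at least one component, and no evidence of progressive disease"; progression anywhere rules it out. Overall CR requires CR in every involved component; catecholamines are not mentioned.

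**Overall response, tables of 10.7.1.** Table 8, "Overall Response for Patients with Neuroblastoma and Measurable Disease", and Table 9 (MIBG-positive disease) give overall PR when the marrow entry is merely non-progressive. Neither has a minor-response row. In both, the CR row requires normal catecholamines, and elevated catecholamines turn an otherwise complete response into PR.

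**Marrow categories, 10.7.** Marrow SD is infiltration that stays above 5% "but does not meet CR, MD, or PD criteria", so it is a non-progressive state. A general sentence calls any infiltration above 0 and up to 5% minimal disease (MD). The MD bullets cover baselines of none, up to 5%, and above 20%; the last reads "BM with > 20% tumour infiltration that has > 0 to" an upper limit of 5%.

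**Catecholamines.** 10.6: "Urine catecholamine levels will not be used to evaluate response because of a lack of standardization in specimen collection and analysis". 10.4.2, under CR: "Normalization of urinary catecholamines or other tumour markers if elevated at study enrollment (for patients with neuroblastoma").

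**MIBG, 10.6.3.** Bone PR is a fall of at least "50% reduction in MIBG absolute bone score (relative MIBG bone score" from 0.1 to 0.5). CR needs complete resolution of uptake.

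**The concern.** The primary endpoint counts CR plus PR; a minor response does not count. Both the 10.7.1 text and its tables are operative, because the text refers the reader to the tables for details and neither is given precedence. 10.6.2 and 10.6.3 make central review the source of the efficacy result for MIBG lesions, so reviewers need one rule.

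Section 11 closes either cohort at 1 or fewer responses in 10, and rejects the null at 5 of 20 (Cohort A) or 6 of 30 (Cohort B). When a count lies next to one of these limits, reclassifying one patient changes the decision. The catecholamine and MIBG conflicts add cases in which the category depends on which sentence is applied.

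**Working it through.** These are classification rules, so the plan has no figure to reproduce. The check sets the rules side by side.

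**1. One patient under both rules (no progression anywhere).**

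| Soft tissue | MIBG | Marrow | 10.7.1 text | Table 8 |
|---|---|---|---|---|
| PR | PR | SD | Minor response: non-responder | PR: responder |

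Table 9 also gives PR when MIBG is PR, there is no new lesion and the marrow is non-progressive.

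**2. All non-progressive combinations, text against Table 8.** Soft tissue (CR, PR, SD) × MIBG (CR, PR, SD) × marrow (CR, MD, SD) × catecholamines (normal, elevated, not done) = 3 × 3 × 3 × 3 = 81. Two reading assumptions: CR in a component satisfies a requirement for PR, and a combination without a table row is not counted as a responder by the table.

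- Marrow SD, minor response by text and PR by Table 8: soft tissue/MIBG of CR/PR, PR/CR or PR/PR, each with three catecholamine states (9), plus CR/CR with elevated catecholamines (1). Total 10.
- Responder by text, no row in Table 8: CR/CR/CR with catecholamines not done; CR/CR/MD with catecholamines normal; CR/CR/MD with catecholamines not done. Total 3.
- Sum: 10 + 3 = 13 of 81 differ in ORR status.

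CR/CR/CR with elevated catecholamines is CR by text and PR by Table 8, which leaves ORR unchanged. CR/CR/MD is PR in Table 8 if catecholamines are elevated, yet has no row if they are normal. These counts are rule combinations, not expected patient frequencies.

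**3. MIBG.** With baseline score b and follow-up score f, the relative score is f/b. Nine bone sectors scored 0 to 3 give a maximum of 27; the tenth, extra-osseous sector makes it 30. For 0 < f/b < 0.1 in whole numbers:

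- f = 1 needs b ≥ 11, since 1/11 = 0.091 (a fall of 90.9%).
- f = 2 needs b ≥ 21, since 2/21 = 0.095 (a fall of 90.5%).
- f = 3 would need b above 30, which is off the scale.

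That is 17 + 7 = 24 score pairs on the 27-point scale and 20 + 10 = 30 on the 30-point scale. Every one is a fall of more than 90%. Each meets the requirement of at least a 50% reduction and fails the bracketed range, and none is CR.

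**4. Marrow bullets.** A fall from, say, 12% to 3% fits no MD bullet, and it is not SD because it is no longer above 5%. The general sentence in 10.7 makes it MD. MD is allowed for PR by the text, and 3% is non-progressive in the tables, so no ORR effect is expected.

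**The case against.** The strongest reply is that the conflict is narrow. It needs a neuroblastoma patient whose marrow stays above 5% while disease responds elsewhere, and a cohort count next to a limit. Section 1.1 lists neuroblastoma among tumours reported in fewer than five cases in CMMRD. Section 1.7 does name it among hypermutant diagnoses, but no number is planned. This limits the size; it does not remove the contradiction.

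Three stronger readings are tempting, and the protocol does not support them:

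- **A neuroblastoma CR can never be assigned, because the 8.2 calendar names no catecholamine test.** The 10.7.1 text gives a CR rule without catecholamines, and the 10.4.2 clause applies only if they were elevated at enrolment. Footnote 12 of 8.2 makes evaluations depend on diagnosis and points to Section 10; MIBG is not named in the calendar either. With a known result and CR in all components, only CR versus PR is at stake.
- **Deep MIBG responses are excluded from PR.** The same sentence also asks for at least a 50% reduction, which they meet. It contradicts itself; it does not clearly exclude them.
- **Marrow falling from between 5% and 20% to 5% or less has no category.** The general sentence in 10.7 supplies one; the bullet is merely narrower.

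It is also fair to say that nothing in the protocol shows whether text or tables should govern.

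**Conclusion.** The inconsistency is real and reaches the primary endpoint. The main point is marrow SD: non-responder by text, responder by table, accounting for 10 of the 13 combinations that differ. Catecholamines come second: they mostly move CR versus PR, but they leave three combinations that the text counts as responses without a Table 8 row. The MIBG sentence is third, for relative scores above 0 and below 0.1, reachable only from a baseline of 11 or more. The MD bullet is a minor alignment.

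The effect on the ORR estimate cannot be sized, because the number of neuroblastoma patients is not stated; it may be small. The conclusion rests on reading component CR as satisfying a requirement for PR, and on the tables having no precedence over the text.

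**What to change.** Adopt one algorithm for neuroblastoma and state that it governs. Following the 10.7.1 text, the changes are:

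- In the PR rows of Tables 8 and 9 with PR in soft tissue or MIBG, set marrow to CR, MD or not involved.
- Replace the row that gives PR for complete imaging response with elevated catecholamines (both tables) by one with marrow MD giving PR.
- In the CR rows, set marrow to CR or not involved. With the row above replaced, CR in all components then maps to CR only.
- Add a minor-response row, marked as non-responder, for marrow SD with PR or CR elsewhere and no progression. Limit the existing SD rows so that they do not overlap with it; both are non-responders, so ORR is untouched.
- Remove the catecholamine column and the catecholamine clause in 10.4.2. State that the tumour-marker rules in 10.3.5 and 10.4.3 do not apply to urine catecholamines in neuroblastoma.
- Write the MIBG criterion for PR as a relative score of 0.5 or less, with CR assigned first.
- Change the third MD bullet to a baseline above 5%.

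If the sponsor prefers the tables to govern, the text of 10.7.1 and 10.6 must be changed to match.

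The cost is wording in Section 10, with no new visits or samples. Under the text-based version slightly fewer patients may count as PR, because marrow SD no longer qualifies.
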